enrolling site, with the case report forms faxed to the Principal Investigator at the University California San Diego using a secure fax machine in a locked office to protect personal health information. All data collection following the day of surgery will occur by telephone from the University of California San Diego, which will then enter all data to the database. For the UG3 feasibility study, the final data collection point for each subject will be at 4 months following surgery (the 12-month time point will be used for the definitive UH3 pragmatic clinical trial). Quality assurance will be ongoing by the University of California San Diego, which will monitor data for sources of error and report to the Medical Monitor (DSMB Chair) with written monthly reports. Each enrolling center will be expected to enroll at least 1 subject for each of the 3 possible lead locations (e.g., brachial plexus trunks) in each of the first two quarters of the 2nd year of the funding period. Combined, the 7 centers will enroll a total of 64 subjects as part of the feasibility study.

Preparation for the UH3 Clinical Trial. If one or more centers fails to enroll their designated subjects—for whatever reason(s)—other centers will make up this enrollment with coordination by the Principal Investigator. The 64-subject feasibility study will enable evaluation of the study intervention, protocol, case report forms, outcome measures, data-entry platform, Research Coordinators, Site Directors, and study oversight. Any changes deemed necessary by the Principal Investigator in concert with the DSMB, funding agency, Steering Committee, Site Directors and NIH-DoD-VA Pain Management Collaboratory Coordinating Center will be made to any aspect of the study design (such as the outcome measures or informed consent forms), including replacing any enrolling center that fails to demonstrate the ability to adequately enroll and execute the protocol. The data from the first 64 subjects will be cleaned by University of California San Diego and a statistical analysis performed by the study statistician ([name]) at the Department of Outcomes Research (Cleveland Clinic).

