Definitive information about the execution of the intervention will be collected by the Primary Investigator and provided to the funding agency (any deficiencies will be corrected with the Site Directors). As with the feasibility study, monitoring of all Sites will continue by the Primary Investigator, with monthly reports provided to the Medical Monitor (DSMB Chair), reports provided to the DSBM every 6 months (unless the DSMB charter specifies a different duration), and to the funding agency / oversight body annually. The IRB continuing reviews will occur annually at the enrolling centers. Clinicaltrials.gov registry will remain up-to-date. We will continue to work closely with the NIH-DoD-VA Pain Management Collaboratory Coordinating Center regarding all aspects of the project.

Year 3 Milestones [Implementation Phase Year 1]:

- o Re-initiate enrollment with revised protocol
- o Successfully enroll a total of 48 subjects during each quarter, for a total of 192 subjects over the course of the year, divided approximately by anatomic lead location (e.g., 33% sciatic lead subjects)
- o Successfully upload to the data-collection platform (database) all data from UH3 clinical trial subjects
- o First interim analysis after 25% of subjects enrolled
- o Approval by all regulatory bodies (DSMB, local IRBs, funding agency's regulatory body)

Year 4 Milestones:

- o Successfully enroll a total of 48 subjects during each quarter, for a total of 192 subjects over the course of the year
- o Successfully upload to the data-collection platform (database) all data from UH3 clinical trial subjects
- o Second interim analysis after 50% of subjects enrolled
- o Approval by all regulatory bodies (DSMB, local IRBs, funding agency's regulatory body)

Year 5 Milestones:

- o Successfully enroll a total of 48 subjects during each of the first 3 quarters, for a total of 144 subjects over the course of the year (Principal Investigator to work with all centers to ensure an equal number of total subjects with each anatomic lead location)
- o Successfully upload to the data-collection platform (database) all data from UH3 clinical trial subjects
- o Third interim analysis after 75% of subjects enrolled
- o Conclusion of enrollment anticipated in the third quarter
- o Approval by all regulatory bodies (DSMB, local IRBs, funding agency)
- o Clinicaltrials.gov updated

Year 6 Milestones:

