0.263 versus HA: $\mu_1 - \mu_2 < \log(1.2) = 0.263$, where μ_1 and μ_2 are the means of log-transformed opioid consumption for PNS and usual care, respectively, and $\mu_1 - \mu_2$ is estimated by the coefficient (i.e., beta) for PNS versus usual care in the regression model. The estimated treatment effect beta will also be an estimate of the ratio of geometric means for the two groups, assuming data for each group is log-normal with similar coefficient of variation between groups.

In the planning phase, focus will be on the estimated confidence interval for the treatment effects and the variability of the outcomes.

Secondary outcomes will be assessed using appropriate statistical methods. We will use the t-test or Wilcoxon rank sum test for physical and functioning as measured by the Brief Pain Inventory (Hypothesis 3), chi-square analyses and t-test of Wilcoxon rank sum test for incidence and intensity of chronic pain, respectively (Hypothesis 4), and Wilcoxon rank sum for quality of life measure by the World Health Organization Quality of Life-BREF Instrument.

[figure not shown]
Subgroup analysis for gender and ethnicity. There is little relevant prior experience with the study intervention in the patient population of the proposed investigation, so it is not known whether either gender or ethnicity would interact with the treatment effect. Therefore, in accord with the Human Subjects recommendations, we will assess the treatment effect of PNS on each outcome of interest within gender and ethnicity subgroups. In addition, we will analyze each anatomic location to detect variations in treatment effect among the various lead insertion sites and types of surgical procedures. We will not require a significant interaction between treatment effect and these factors, but will rather conduct the subgroup analyses for each level of sufficient size (n=30). The subgroup analyses will be the same as those conducted on the entire sample, and so would be just as valid and unbiased.

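### Variation in effect among lead locations is to be sought through separate within-location analyses, with no interaction test specified, and significance verdicts compared across locations do not test variation

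*Combined protocol and SAP*

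**What the plan says.** The paragraph on subgroup analysis for gender and ethnicity (section 9, Statistical Plan and Data Analysis) gives two aims. For gender and ethnicity: "we will assess the treatment effect of PNS on each outcome of interest within gender and ethnicity subgroups". For lead location: "we will analyze each anatomic location to detect variations in treatment effect among the various lead insertion sites and types of surgical procedures".

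The method is the same for all three factors. The plan states "We will not require a significant interaction between treatment effect and these factors", and says that it will instead "conduct the subgroup analyses for each level of sufficient size (n=30"). It then defends this: "The subgroup analyses will be the same as those conducted on the entire sample, and so would be just as valid and unbiased".

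The UH3 text says that its methods follow the UG3 methods closely and that UH3 will have enough data for the subgroup analyses. The UH3 sample size, however, is worked out for the whole trial only. In UG3, 64 subjects over three locations is about 21 each, below the limit of 30, so the location analysis is in practice a UH3 analysis. The only interaction named elsewhere is treatment by time in the pain model. No multiplicity rule and no rule for reading subgroup results that differ is given.

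**The concern.** An analysis within one location asks whether there is an effect there. Whether the effect varies among locations is a different question, and only a comparison between locations answers it. The plan states the second question for lead location and specifies only the first kind of analysis.

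Each location holds about a third of the subjects, so its power can be far below the 90% planned for the trial. When power per location is moderate, a mixture of significant and non-significant locations is an ordinary result even if the true effect is the same everywhere. The trial pools different nerves and operations. A mixed pattern could be taken to mean that stimulation works after one operation and not after another, and the sentence on equal validity encourages that reading.

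**Working it through.** **Inputs, all from section 9.** Lead locations: "each of the 3 possible lead locations" (UG3 enrollment). Equal sizes: the Year 5 milestones ask the centers to "ensure an equal number of total subjects with each anatomic lead location". With total N=528 and 1:1 allocation, this gives 528/3 = 176 per location, 88 per arm. Opioids: 20% reduction, CV 0.75. Pain: 1 point, SD 2. Significance level: 0.0125 one-sided for each superiority test in the sample-size text, 0.05 in the general statement. The plan does not say which applies to subgroups, so 0.0125, 0.025 and 0.05 (one-sided) are all shown.

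**Reproducing the plan's N.** On the natural-log scale the effect is |ln 0.8| = 0.223 and the SD is √ln(1+0.75²) = 0.668, so the standardized effect is 0.223/0.668 = 0.334. The number per arm is 2(2.241+1.282)²/0.334², about 223, or 446 in total; the noncentral t gives 448, the stated figure. A four-look design with the stated spending parameters and non-binding futility inflates this by 1.174 to about 526, against the stated 528. CV 0.65 would give 352 and CV 1.0 would give 692, so 0.75 is the CV behind the stated N.

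**Power in one location.** p = Φ(d√(n/2) − z), with n = 88 per arm and √(88/2) = 6.633. For opioids d√(n/2) = 0.334 × 6.633 = 2.216; for pain 0.5 × 6.633 = 3.317.

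**Chance that some but not all of three locations are significant when the true effect is identical:** 1 − p³ − (1−p)³. With equal power this cannot exceed 75%, reached at p = 0.5.

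| Outcome | One-sided level | Power per location | Mixed verdicts |
|---|---|---|---|
| Opioids, CV 0.75 | 0.0125 | 49% | 75% |
| | 0.025 | 60% | 72% |
| | 0.05 | 72% | 61% |
| Pain, 1 point | 0.0125 | 86% | 36% |
| | 0.025 | 91% | 24% |
| | 0.05 | 95% | 14% |

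Example, opioids at 0.025: 1 − 0.601³ − 0.399³ = 1 − 0.217 − 0.064 = 0.719.

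**Sensitivity.** On opioids, mixed verdicts are 15-40% at CV 0.48 (the plan's preliminary data), 48-72% at CV 0.65 and 65-74% at CV 1.0. On pain with a true effect of 0.5 point they are 61-75%. With no effect at all they are 4-14% per outcome.

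**Joint rule repeated in each location** (superior on at least one outcome and noninferior on the other; simulated, outcome correlation assumed 0 to 0.7 because the plan gives none). If both design effects hold, mixed verdicts are 22-35% with superiority at 0.0125 and 6-13% at 0.05. If only opioids have their effect, the figure is about 75% at 0.0125.

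**A level of 30 subjects** (15 per arm, √(15/2) = 2.739). Opioids: 0.334 × 2.739 = 0.915, power 9%, 15% and 23% at the three levels. Pain: 0.5 × 2.739 = 1.369, power 19%, 28% and 39%.

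**The alternative.** A 2-df treatment-by-location test at 0.05 declares a false difference in 5% of trials per outcome, whatever the common effect. In simulation, only 7% of the mixed opioid results (one-sided 0.025) also had interaction p<0.05. Its power is limited. The standard error per location is 0.668 × √(2/88) = 0.1007. With effects −0.223, −0.223 and 0, the squared deviations from their mean sum to 0.0332, the noncentrality is 0.0332/0.1007² = 3.27, and power is about 35%.

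**The case against.** Several stronger readings are tempting, and the documents do not support them.

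- **That false differences between locations will usually appear.** This fits opioid consumption at the design CV, but not opioids at CV 0.48, pain at the planned effect, or the joint rule when both design effects hold. The joint rule matters because the subgroup analyses are to repeat those of the whole sample.
- **That the plan forbids an interaction test.** It says that a significant interaction is not required. One could still be fitted, although the wording presents separate analyses as the substitute.
- **That differing verdicts will be reported as a difference.** No sentence says so. The step from mixed significance to a claimed difference is an inference, which the plan leaves open by giving no rule.
- **That the subgroup estimates are biased.** Randomization is stratified by lead location, so each within-location estimate is unbiased, and low power does not change that. This part of the plan's defense stands.
- **That the aim of detecting variation covers all three factors.** It is stated only for lead location. For gender and ethnicity the plan speaks of effects within subgroups.
- **That an overall false-positive rate can be quoted.** The number of subgroup tests is not stated and the tests share patients, so no such figure follows from the documents.

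It is also fair to object that the interaction test is weak here. That is a reason to report estimates and intervals beside it. It does not make a comparison of verdicts valid.

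**Conclusion.** The concern holds for lead location: the method specified cannot answer the question asked, and the sentence on equal validity hides this. On opioid consumption, the endpoint that sets N, mixed verdicts would occur in about 61-75% of trials with no true difference between locations at the design CV. The other settings worked through range from 4% to 75%, depending on outcome, CV, true effect and decision rule.

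These figures assume three equal, independent locations, no dropout, and full enrollment of 528. An early stop would leave fewer subjects per location and is not modeled here. With unequal locations of 264, 176 and 88, the opioid figure at 0.025 is 78%. The whole-trial primary claim is not affected, so this is a change that should be made but does not threaten the main result.

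**What to change.** 1. Prespecify a treatment-by-location interaction test (2 df, with location main effects) in the opioid and pain models. Do the same for gender and ethnicity if any difference between their levels is to be claimed.
2. Base any claim of a difference between levels on that test.
3. Show subgroup estimates with confidence intervals, labeled exploratory, and use the limit of 30 only to decide which levels are displayed.
4. Delete the sentence asserting that subgroup analyses are as valid as the whole-sample ones.
5. State that a non-significant interaction is not evidence of equal effects, given power of about 35% when one location has no effect and the others have the 20% reduction.

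The cost is SAP wording and somewhat larger models: the primary models now hold only treatment, plus time for pain, so factor main effects must be added as well as the interaction. Outcomes planned for rank-sum or chi-square tests have no model to extend and would need one if a difference between levels were to be claimed on them. Fewer subgroup p-values would be reported. No added subjects or visits are needed.

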Planning Phase sample size considerations. The sample size for the planning phase of 64 patients will be sufficient to estimate the treatment effects of interest with moderate precision, i.e., a confidence interval width of roughly 1.1 standard deviations for each outcome measure. Confidence interval width for a standard deviation estimate will be 0.70 standard deviations. The planning phase will be sufficient to use in estimating the expected treatment effect and standard deviation for each outcome for the larger trial.

UH3 Implementation Phase. Statistical methods for the UH3 Implementation Phase will follow very closely the methods described for the UG3 Planning Phase. The main difference is that UH3 Implementation Phase will have sufficient data to conduct the subgroup analyses and also considerably more power to assess the treatment effects of interest.

Another substantive difference from the planning phase is that in the full trial we will conduct interim analyses at each 25% of the planned enrollment using a group sequential method with gamma spending function and gamma parameter of -4 (quite conservative) for efficacy and 0 (moderately aggressive) for futility (**Figure 14**). The probability of crossing a boundary for either efficacy (mainly) or futility at the first through fourth looks would be 0.10, 0.42, 0.80 and 1.0, respectively, assuming the alternative hypotheses were true.

Figure 14. Stopping boundaries for 1-tailed tests for superiority for either pain score or opioid consumption. Blue region indicates superiority (reduced opioid consumption or pain score) and pink region indicates futility (lack of superiority). Z-statistic represents strength of evidence against the null hypothesis, either ratio of means or difference in means divided by standard error.

Missing outcomes data will be summarized along with the etiology of the absence. | While very little outcomes data is expected to be missing,

analyses will be intention to treat, and imputation of missing data using methods such as multiple imputation and last observation carried forward will therefore be utilized, based on the situation. In a conservative analysis imputation will involve the conservative approach of assigning the worst observed outcome to patients in intervention groups and best observed outcomes to those in control.

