Throughout, the significance level will be 0.05 for each hypothesis. SAS statistical software (Cary, NC) will be used for all analyses, and East 6.0 (Cytel, Inc. Cambridge, MA) for interim monitoring and sample size calculations.

UH3 Implementation Phase sample size considerations. Sample size parameters for the implementation phase will be derived from estimates in the planning phase. The sample size calculations below are conservative in that we observed a coefficient of variation for opioid consumption observed in our preliminary data of 0.48, substantially better than the assumed 0.65. It is thus quite possible that the actual sample size for the implementation phase will be smaller.

Sample size for the full trial will be chosen to allow an overall 90% power at the 0.025 significance level (since 1-tailed tests) to claim the intervention more effective than the control on postoperative opioid requirements and pain as measured by NRS pain score. In our joint hypothesis testing on these two outcomes, we power the study to have overall 90% power to detect superiority on either

outcome and at least noninferiority on both. We assume a coefficient of variation of 1.0 for opioid consumption and a standard deviation of 2 for pain score.

Power for the joint hypothesis testing will be driven by superiority tests since superiority is needed for at least 1 of the 2 outcomes. For cumulative opioid consumption through POD 3 our previous data had a coefficient of variation (CV) of 46% (mean (SD) of 28 (13) mg). Conservatively assuming a coefficient of variation of 75% through 7 days,¹⁸³ with a total N=528 we would have 90% power to detect a relative reduction of 20% in mean opioid consumption at the overall 0.025 significance level (0.0125 for each of the two 1-tailed tests for superiority), adjusting for interim analyses (N=448 before adjustment for interim analyses).

This sample size will yield high power (>0.95%) to detect superiority based on the intervention group having 1 point or more better than the control group on NRS pain score within the first 7 days, assuming a standard deviation of 2 points for mean of the “average” pain score for each patient.

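### UH3 adds efficacy and futility stopping but keeps fixed-sample effect estimates; at the design effect this gives a modest bias and about 91% interval coverage, and the plan names no adjusted estimate

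*Combined protocol and SAP*

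**What the plan says.** All of this is in Section 9 of the combined protocol and SAP, under Statistical Plan and Data Analysis.

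- **Stopping.** The UH3 Implementation Phase text says "we will conduct interim analyses at each 25% of the planned enrollment using a group sequential method", with a "gamma spending function and gamma parameter of -4 (quite conservative) for efficacy and 0 (moderately aggressive) for futility". The cumulative probabilities of crossing either boundary "at the first through fourth looks would be 0.10, 0.42, 0.80 and 1.0, respectively, assuming the alternative hypotheses were true". The caption of Figure 14 applies the boundaries to superiority on either pain or opioids.
- **Estimation.** "Statistical methods for the UH3 Implementation Phase will follow very closely the methods described for the UG3 Planning Phase". In the UG3 text, log cumulative opioid dose is analysed by simple linear regression, and the group difference "is estimated by the coefficient (i.e., beta) for PNS versus usual care in the regression model". Pain uses the treatment coefficient of a linear mixed model. UG3 has no interim looks.
- **Software.** The group-sequential package is "East 6.0 (Cytel, Inc. Cambridge, MA) for interim monitoring and sample size calculations". Estimation is not among its tasks.
- **Size.** The UH3 sample size text says "with a total N=528 we would have 90% power to detect a relative reduction of 20% in mean opioid consumption", and sets the test "at the overall 0.025 significance level (0.0125 for each of the two 1-tailed tests for superiority").

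No bias-adjusted, median-unbiased or repeated-interval method is named. Confidence intervals are mentioned only for the planning phase, and no interval or level is stated for UH3.

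**The concern.** The boundaries protect the type I error of the superiority test. They do nothing for the estimate. A trial that stops because it crossed an efficacy boundary has been selected for a large observed effect, and one that stops for futility has been selected for a small one. A regression coefficient computed as if the sample size had been fixed ignores that selection, and so does its interval.

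The size of the opioid reduction is the main message of this trial. By the plan's own crossing probabilities, 80% of trials would stop before the final look under the alternative, so an estimate made after early stopping is the likely one to be published.

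**Working it through.** **Inputs.** From the plan: four looks at 25, 50, 75 and 100%; gamma -4 efficacy and gamma 0 futility spending; one-sided 0.0125 per outcome; 90% power; ratio 0.80; CV 0.75; 1:1 allocation; N=448 before and 528 after adjustment for looks. My assumptions: equal information between looks, no overrun, and non-binding futility boundaries that are followed in practice.

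**Fixed design.** Log-scale SD = sqrt(ln(1 + 0.75²)) = 0.668. Per arm, 2 × (2.241 + 1.282)² × 0.668² / (ln 0.8)² gives 223, so 446 in total (stated 448). The CVs of 0.65 and 1.0 that also appear in the sample size text give 352 and 692, so 0.75 is the value behind the plan's figure.

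**Sequential design.** Numerical integration with non-binding futility gives an inflation of 1.1766, and 448 × 1.1766 = 527 (stated 528). Binding futility gives 503. Cumulative crossing probabilities are 0.100, 0.425, 0.810 and 1.0 (stated 0.10, 0.42, 0.80 and 1.0). The design is reproduced.

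**What a crossing requires.** The efficacy bounds are Z = 3.352, 3.038, 2.687 and 2.299. The SE of the log ratio is 0.668 × sqrt(4/528) = 0.058 at full enrolment, and 0.116, 0.082 and 0.067 at looks 1 to 3. The observed ratio must be at or below exp(-Z × SE) = 0.677, 0.779, 0.835 and 0.875.

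**Plain estimate at the design effect, opioids alone** (simulation, 1 to 2 million trials per scenario):

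- Early efficacy stops: 0.075 + 0.300 + 0.360 = 73.5%. Early futility stops: 7.5%.
- Mean log effect over all trials is +7%: exp(1.07 × ln 0.8) = about 0.787.
- Among early efficacy stops it is +25%, a ratio of about 0.757. By look it is +99%, +34% and +1%, so the exaggeration sits at looks 1 and 2.
- A plain 95% interval covers 90.8% over all trials.

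**Where the coverage is lost.** Intervals after early efficacy stops cover 95.3%. With efficacy stopping only, overall coverage is 94.0%. Futility stopping therefore accounts for 94.0 - 90.8 = 3.2 of the 95.0 - 90.8 = 4.2 points lost.

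**Other true effects, as multiples of the design log effect:**

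| Multiple | Early efficacy stop | Mean bias of log effect | Plain 95% coverage |
|---|---|---|---|
| 0 | 0.4% | mean ratio about 1.03 | 95.7% |
| 0.5 | 16% | -20% | 93.1% |
| 0.75 | 42% | -1% | 91.9% |
| 1 | 73% | +7% | 90.8% |
| 1.25 | 93% | +9% | 94.1% |
| 1.5 | 99% | +8% | 95.3% |

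At half the effect, the 16% that stop early for efficacy report a log effect 2.1 times the truth, even though the average over all trials is too small.

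**Stopping on either outcome.** The correlation between outcomes is not given, so I used 0 to 0.6. I let futility stop the trial only when both outcomes fall below their bounds. If pain has the same drift as opioids, early efficacy stops rise to 86-93%. At the planned 1-point pain effect with SD 2, they are about 99%. Across those cases opioid bias is +3% to +9% and coverage is 93.5-94.9%. If pain has no effect, opioid coverage is 90.9-91.9%.

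**Effect of adjusting.** In 4,000 simulated trials at the design effect (opioids alone), the stage-wise estimate had a median of 0.99 and a mean of 1.02 times the truth, with 94.8% coverage. The plain estimate in the same trials averaged 1.06 times the truth. For results exactly on the efficacy boundary:

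| Look | Plain ratio (95% interval) | Adjusted ratio (95% interval) |
|---|---|---|
| 1 | 0.676 (0.538-0.850) | 0.676 (0.538-0.850) |
| 2 | 0.778 (0.662-0.915) | 0.779 (0.663-0.918) |
| 3 | 0.834 (0.731-0.952) | 0.835 (0.730-0.955) |
| 4 | 0.874 (0.780-0.980) | 0.868 (0.764-0.979) |

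An ordering that ignores the futility boundary reaches only about 92% coverage at the design effect.

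**The case against.** The strongest reply is that this is a reporting refinement argued partly from silence. UH3 promises no 95% interval, and its methods are to follow UG3 closely rather than identically. Section 9 also says, under Preparation for the UH3 Clinical Trial, that the statistical section will be revised after the pilot. Superiority is judged against proper boundaries, so no decision changes. Average bias at the design effect is about 1.3 percentage points of reduction, and the adjustment barely moves results near a boundary. All of that stands. What remains is that the only estimators named are fixed-sample ones and that the plan names nothing to replace them.

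Three stronger readings are tempting, and the documents do not support them:

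- A reader might infer that the trial will stop early for efficacy about 74% of the time. That holds only if the 20% reduction is true and opioids are monitored alone. The plan's crossing probabilities are conditional on the alternative and combine efficacy with futility.
- A reader might infer that early efficacy stopping is what makes the interval under-cover. At the design effect, intervals after early efficacy stops cover 95.3%. Most of the shortfall comes from futility stops.
- A reader might infer that the reported effect will be exaggerated whatever the truth. Averaged over all trials, the bias is close to nil at three quarters of the design effect and toward the null at half.

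**Conclusion.** The point holds in a limited form. The plan joins a four-look design with efficacy and futility stopping to plain estimates that ignore stopping. If followed as written, the opioid estimate at the design effect averages about 7% too large on the log scale. The exaggeration is concentrated in stops at looks 1 and 2, and a plain 95% interval covers about 91%. With either-outcome stopping and a working pain effect, coverage is about 93.5-95%.

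These figures rest on CV 0.75, N=528, one-sided 0.0125, followed non-binding futility, equal information and, for two outcomes, assumed correlations. The 95% level is also my assumption. An interval matched to one-sided 0.0125 would be 97.5%, and its plain version covers 95.9% at the design effect with opioids alone. The type I error and the superiority claim are untouched.

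**What to change.** State in the UH3 analysis section, before any interim look, that each primary outcome will be reported with:

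- a median-unbiased estimate and a stage-wise-ordering 95% confidence interval, the ordering to cover both the efficacy and the futility boundaries actually followed;
- the plain regression or mixed-model estimate alongside;
- for a stop at look 1 or 2, a stated caution that the estimate is probably exaggerated. The adjustment cannot remove this: at look 1 the adjusted and plain figures coincide.

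Say also whether futility is binding, and how the ordering is applied to an outcome that did not itself trigger the stop. The 94.8% coverage above was checked for one outcome monitored alone.

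The cost is a few sentences and one extra output, and usually a slightly smaller effect or wider interval after an early efficacy stop. Fixing the method in advance also prevents a later choice between two sets of figures.
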